randomized to FORT-A will complete the standardized FORT-A Program (described in detail below). All participants will complete a standardized battery of assessments at pre-treatment (Week 0), post-treatment (Week 4/5), 6-month follow-up (Week 30/31) and 12-month follow-up (Week 56/57; see Figure 1, below).

Interventions and Duration

FORT-A: An amended version of the military Functional Orthopedic Rehabilitation Treatment (FORT) program. For FORT-A, CBT components of FORT were diminished and replaced with mindfulness and Acceptance and Commitment Therapy (ACT) components. Individual FORT treatment sessions have been altered in FORT-A to focus on PTSD symptom management using an abbreviated, manualized Prolonged Exposure treatment. FORT-A includes:

- 12 sessions (90-minutes each) of manualized group pain management
- 12 sessions (90-minutes each) of group-based functional restoration Physical Therapy
- 6 sessions (75 minutes each) of individual psychotherapy for pain and PTSD
- 6 sessions (30 minutes each) of biofeedback for pain management
- Weekly interdisciplinary case staffings

PRC: The STVHCS PRC is the only self-contained PRC in the VA’s nationwide Polytrauma System of Care. The PRC is an interdisciplinary treatment center including: interdisciplinary assessment and treatment, case management, mental health support, physical medicine and rehabilitation (PM&R), physical therapy, speech therapy, prosthetists/orthotists, and other integrated specialty services. The PRC sees approximately 30 new patients each month, most of whom (80%) present with a chronic service-related musculoskeletal pain condition and military trauma comorbidity (traumatic brain injury [TBI], PTSD, depression). Though individual treatment plans may vary, most PRC Veterans will complete up to 12 sessions of Physical Therapy and be followed by a PM&R physician for pain and other symptom management. Pain management with PM&R may include medications, injections, and other palliative medical interventions. The PM&R physicians may also make recommendations about physical function, health behaviors, and mobility.

Sample Size and Population

This research study will include 130 OEF/OIF/OND Veterans who meet the following criteria:

- Present with an ongoing chronic musculoskeletal condition (pain that has been a problem for more than half the days over the past three months) documented in the CPRS record or confirmed by a PM&R physician upon referral to the PRC

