3. STUDY DESIGN

To address the primary and secondary hypotheses, this research study was designed as a randomized clinical trial comparing the manualized FORT-A treatment to treatment as usual for polytraumatic chronic musculoskeletal pain in the STVHCS Polytrauma Rehabilitation Center. Eligible OEF/OIF/OND Veterans will be randomized to either arm in 1:1 random permuted block randomization with no stratification. Because the FORT-A is a group intervention, it is vital that we randomize into meaningful blocks of at least three Veterans and no more than seven. Three is chosen as the lower block boundary because the PI had success in the original FORT trial with FORT groups of three active duty service members. Seven Veterans will be the upper boundary because FORT groups of more than seven military members were difficult to manage. In block randomization with static boundaries, study staff overseeing randomization will lose blinding if they are aware of how many participants have already been randomized into each block. For example, if block boundaries are always 5 participants and the treatment as usual condition has 5 participants while the active treatment has 4, then the staff randomizing the 10th participant will know with certainty that this participant will be in the active treatment group. To protect blinding, we have chosen to implement a variable boundary randomization for which the study staff randomizing patients will be blind to the boundaries and the resulting condition of the participant (see Sanghaei, 2011). The PI, Independent Evaluators, and Biostatistician will be blind to the condition of all participants until data lock. A research assistant overseeing randomization will also be blinded by randomizing unique patient identifiers into variable permuted blocks (through the STRONG STAR Data Core) by unique study identifier (e.g., first participant identified as #0001). All assessments given by Independent Evaluators will be labeled with just the unique identifier. Only the study coordinator (and co-coordinator) will be able to link unique identifiers to individual participants.

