5. STUDY INTERVENTIONS

5.1 Interventions, Administration, and Duration

FORT-A

Although pain programs like FORT-A have been explored in civilian pain populations ([name] et al., 2006; Mayer et al., 2004; Proctor et al., 2004), military and Veteran research has been limited. FORT-A is a particularly good fit for military and Veteran populations because the focus of treatment is on return to function, not on palliative pain relief. This works well for military and Veteran pain sufferers who are used to “biting back” pain and pressing on with their mission. When we first developed the FORT program, we included a number of newly emerging complementary and alternative medicine interventions that were starting to show promise in pain research (mindfulness, biofeedback, relaxation strategies, motivational interviewing, acceptance and commitment therapy, guided exercise and activity – including mind-body exercises like yoga). Outcomes from our DoD-funded study of FORT revealed significant improvements in pain management (Gatchel et al., 2009). CAM interventions have been strongly emphasized in the FORT-A manual (see Appendix) based on participant feedback from the original FORT trial and from research subsequent to the FORT study demonstrating very little beneficial effect of cognitive-behavioral therapy (CBT) for military pain management. We have kept some CBT elements to address cognitive variables that are implicated in psychosocial adjustment to chronic polytrauma pain based on the PI’s current DoD-funded trials (Kanzler et al., 2012). FORT was augmented to include a stronger emphasis on CAM interventions that are most likely to promote pain management and opioid sparing among polymorbid OEF/OIF/OND Veterans, and the augmented program has been labeled “FORT-A.” FORT-A is provided on an outpatient basis and includes 12 daily group pain management and physical therapy sessions spanning three weeks. Group interventions are supplemented by individual psychotherapy, biofeedback, and case staffings. CBT sessions were decreased in favor of CAM components. FORT-A participants will receive 270 minutes (4½ hours) of intervention a day for 12 days over 3 weeks. All FORT-A interventions will occur at the STVHCS PRC in dedicated research space. FORT-A includes: *** 12-session outpatient group intervention.** The FORT-A group occurs 4 times a week for 3 weeks (12 total sessions) for 90 minutes each. Topics include:

- *goal-setting* (2 sessions)

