
All study participants will be offered PRC Physical Therapy before randomization. PRC physical therapy (PT) varies in frequency and duration based on pain presentation, but can occur daily for up to three weeks. PT sessions are individualized, so length of the session will vary from patient to patient.

Potential Adverse Effects (risk): PT may result in muscle soreness (**NOT SERIOUS**) or musculoskeletal injury/worsening of injury (**SERIOUS**)

Not all PRC patients are recommended for, or taken advantage of, the full slate of PRC services (e.g., Family Therapy, Psychology, Occupational Therapy), but all are seen and followed by a Physical Medicine & Rehabilitation Physician and/or Nurse Case Manager at biweekly up to monthly follow-up intervals.

Potential Adverse Effects (risk): Variable (depending on medical or psychological interventions) (**INDETERMINATE**)

The PRC manages chronic pain in accordance with the VA/DoD Clinical Practice Guidelines (CPG; which can be found at <http://www.healthquality.va.gov/>). Interventions for pain management in the PRC may include (but are not limited to) the following based on the CPG (which should be consistent across Polytrauma System of Care sites):

PRC Treatment Component	Adherence Management/Tracking
Diagnostics (Imaging, ESR)	None
Self Care Advice to Remain Active	Consult Chart Interview with Participant
Education Books, Handouts	Consult Chart Interview with Participant
Medication Acetaminophen NSAIDs Antidepressants (TCA) Benzodiazepines Opioids	Consult Chart Opioids and Other Pain Meds: MEMS, Timeline Followback, MQS Interview with Participant
Physical Therapy PT through PRC/PT Service	Consult Chart Functional Capacity Evaluation Interview with Participant
Other Non-Pharmacological Therapy Spinal Manipulation Exercise Therapy Massage Acupuncture Yoga CBT Relaxation Intensive Interdisciplinary Rehabilitation	Consult Chart Interview with Participant

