Depressive Symptom Inventory- Suicidality Subscale (DSI-SS) (suicidal ideation or intent)		Risk Surveillance Suicide risk is not a research endpoint, but if suicide risk is present at a previous assessment (e.g., any positive response for BSSI screening items) then BSSI will be repeated at the next assessment interval (unless participant is disenrolled for a VA mental health treatment referral)
Functional Capacity Evaluation (objective disability)		Endpoint: Hypothesis 2 Assess at all assessment intervals
Pain Catastrophizing Scale (pain-related cognitions)		Endpoint: Hypothesis 2 Variable: Exploratory
Interpersonal Needs Questionnaire (Burdensomeness)		Endpoint: Hypothesis 2 Variable: Exploratory
Fear Avoidance Beliefs Questionnaire		Endpoint: Secondary Objectives Variable: Exploratory
Chronic Pain Acceptance Questionnaire	Endpoint: Secondary Objectives	

		Variable: Exploratory
Multidimensional Pain Inventory		Endpoint: Secondary Objectives Variable: Exploratory
Generalized Anxiety Disorder- 7 item		Endpoint: Hypothesis 2 Assess at all assessment intervals
Current Opioid Misuse Measure		Endpoint: Hypothesis 4 Assess at all assessment intervals
Actiwatch		Endpoint: Hypothesis 2 Assess at all assessment intervals
MEMS eCap		Endpoint: Hypothesis 4 Assess at all assessment intervals
Treatment Helpfulness Questionnaire		Endpoint: Secondary Objectives Variable: Exploratory Only given post-treatment
Subjective Opiate Withdrawal Scale		Endpoint: Hypothesis 4 Assess post-treatment and at follow-ups
Pain Diary		Endpoint: Hypothesis 2 Assess at all assessment intervals
Phone Contact (Adherence/AE/MEMS/Actiwatch)		Treatment Adherence Occurs at all assessment intervals
Quick Drinking Scale (QDS)		Common Data Element with STRONG STAR Studies
Fagerstrom Test for Nicotine Dependence (FTND)		Common Data Element with STRONG STAR Studies
Fagerstrom Test for Nicotine Dependence – Smokeless Tobacco (FTNB-ST)		Common Data Element with STRONG STAR Studies

Randomization

As noted above, participants will be randomly assigned to the FORT-A or PRC on a 1:1 allocation ratio using a randomly selected block size with randomly permuted assignments within blocks.

In the original FORT study we found that the ideal treatment group size for each iteration of the program was 5 participants (though successful groups were able to run with as few of 3 members and as many as 7). Thus, we will attempt to fill treatment

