cohorts for FORT-A and PRC with between 3 to 7 participants (as described in Efrid, 2011). The coordinator and co-coordinator will be blinded to all randomization assignments but will initiate a treatment cohort when a sufficient number of participants have been assigned.

There is a four-week window between enrollment and baseline assessment (Week -4 to Week 0, as shown in 6.1). Study intervention must begin within 2 weeks after baseline to ensure that baseline assessment data adequately represent *current* functioning at the time of treatment, especially functional capacity evaluation [FCE] data that are used to guide the physical therapy portion of the interdisciplinary intervention. Test-retest reliability of FCE has been confirmed over a period of two weeks (Brouwer et al., 2003), with only slight fluctuations in more frequent testing resulting in a slight increase in lifting capacity if repeated across two days, likely due to practice effects (Reneman et al., 2002). Thus, intervention will generally begin within 5 weeks of enrollment.

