9.6 Data Analyses

Data Analysis: To examine our aims and hypotheses we will utilize the generalized linear model, which allows specification of an appropriate distribution for each outcome that can accommodate continuous outcomes (e.g., normal distribution with identity or log link for self-reported disability) and presence/absence outcomes (e.g., binomial with logit link for probability of daily opioid use). We will not stratify our analyses by PTSD or depression, but will account for these variables in our data analysis. Furthermore, we will attend to the influence of missing data on our analyses, and plan on conducting missing values analysis to inform several sensitivity analyses (e.g., LOCF, multiple imputation, etc.) to ensure an intent-to treat principle is observed. Specifically, we will examine the MAR assumption by examining patterns of missingness conditional on baseline assessments, treatment adherence, or other time-varying predictors. Our RCT has one primary endpoint (Oswestry), so both primary and secondary outcomes will be interpreted at a conventional level of statistical significance, $p < 0.05$. To adhere to NIH policy of examining gender and ethnic subgroup analyses, we will add interaction terms (i.e., treatment group x subgroup) for each of our planned analyses. Each analysis is further detailed below:

AIM 1: Assess the efficacy of the FORT-A Program for improved pain management outcomes in (N=130) polymorbid OEF/OIF/OND PRC Veterans with chronic orthopedic pain using a 1:1 randomized clinical trial comparing FORT-A to standard PRC care. To examine our primary hypothesis, we will compare the self-reported disability scores of the two groups at 12-month follow-up while controlling for baseline scores (i.e., an ANCOVA approach). A statistically significant main effect will be interpreted as the groups exhibiting differential change in regards disability. Secondary analyses will use growth curve modeling (mixed effects hierarchical regression with polynomial change parameters) which will model differences in change trajectory over time between the groups across assessment occasions.

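### The primary 12-month ODI ANCOVA ignores FORT-A treatment cohorts of 3 to 7, so its standard error is too small if outcomes correlate within cohorts

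*Combined protocol and SAP*

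**What the plan says.** Group delivery is central to FORT-A. Section 3 says "Because the FORT-A is a group intervention, it is vital that we randomize into meaningful blocks of at least three Veterans". The précis lists "12 sessions (90-minutes each) of group-based functional restoration Physical Therapy", and section 5.1 says of the pain-management component that "The FORT-A group occurs 4 times a week for 3 weeks (12 total sessions) for 90 minutes each". Section 6.2.2 reports from the earlier FORT trial that the "ideal treatment group size for each iteration of the program was 5 participants", and plans to fill "cohorts for FORT-A and PRC with between 3 to 7 participants".

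The comparator is different. Section 5.1 says of the Polytrauma Rehabilitation Center (PRC) that "PT sessions are individualized, so length of the session will vary from patient to patient", and under section 5.1.1 the study gives usual-care participants no second physical therapy recommendation.

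The primary analysis in section 9.6 reads: "we will compare the self-reported disability scores of the two groups at 12-month follow-up while controlling for baseline scores (i.e., an ANCOVA approach". The general framework there is a generalized linear model. The only mixed model for Aim 1 is a secondary growth curve over assessment occasions, with no cohort level. Section 9.2 claims power 0.80 at d = 0.50 (3.3 ODI points, SD 6.6) with 65 per arm and two-sided alpha 0.05. Its effect-size margin of about 60% is tied to imputing missing data, not to clustering.

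**The concern.** This is a partially nested design: one arm is treated in groups and the other, on most of the text, is not. People who spend 24 group sessions together, with the same leaders and each other, may end with more similar outcomes than people treated apart. An ANCOVA with independent errors does not see that similarity. The treatment estimate remains unbiased, but its standard error is too small, so the primary interval is too narrow. If the average effect is zero while cohorts truly differ, the test rejects more than 5% of the time.

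The stated power is affected too. The planned test still rejects at nearly the advertised rate, but partly because its standard error is too small. A test with the right error rate has less power, unless the baseline covariate makes up the difference.

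**Working it through.** **Inputs.** From section 9.2: 65 per arm, SD 6.6, difference 3.3 (3.3/6.6 = 0.50), two-sided 0.05, up to 30% attrition. From section 6.2.2: cohort size m = 3 to 7, typically 5, hence about 65/5 = 13 FORT-A cohorts. Assumed, because the documents give no value: ICC 0.01 to 0.10, and usual-care participants independent.

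**The plan's own figure.** With 65 independent participants per arm and d = 0.50, power is 0.808 (noncentral t) or 0.813 (normal). The stated 0.80 is thus reproduced with no allowance for clustering.

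**Formulas (clustering in FORT-A only).**
- Design effect in FORT-A: D = 1 + (m − 1) × ICC.
- Ratio of true to assumed variance of the difference: VR = (1 + D)/2.
- Actual type I error of the planned test: 2Φ(−1.96/√VR).
- Satterthwaite df: (D + 1)² / [D²/(65/m − 1) + 1/64].
- Interval width, valid against planned: √VR × t(df)/t(128).
- Rejection rate of the planned test at d = 0.50: Φ((0.5 − t(128) × SE_assumed)/SE_true), with SE_assumed = √(2/65) and SE_true = SE_assumed × √VR.
- Power of a valid test: noncentral t with the df above.

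Worked case, m = 5 and ICC 0.05: D = 1 + 4 × 0.05 = 1.20; VR = 2.20/2 = 1.10; √VR = 1.049; type I error = 2Φ(−1.96/1.049) = 0.062; df = 2.20²/(1.44/12 + 1/64) = 36.

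| m = 5 | ICC 0.01 | 0.02 | 0.05 | 0.10 |
|---|---|---|---|---|
| VR | 1.02 | 1.04 | 1.10 | 1.20 |
| Type I error, planned ANCOVA | 5.2% | 5.5% | 6.2% | 7.4% |
| Same, 30% lost at random, completers only | 5.2% | 5.3% | 5.8% | 6.6% |
| Satterthwaite df | 39 | 38 | 36 | 32 |
| Interval ratio, valid/planned | 1.03 | 1.04 | 1.07 | 1.13 |
| Planned test, rejection at d = 0.50 | 0.81 | 0.80 | 0.80 | 0.79 |
| Valid test, power at d = 0.50, no covariate | 0.79 | 0.78 | 0.75 | 0.71 |

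The loss row uses D = 1 + 0.7(m − 1) × ICC. Over m = 3 to 7 without loss, type I error runs from 5.1% (m = 3, ICC 0.01) to 8.6% (m = 7, ICC 0.10).

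**Simulation** (65 per arm, m = 5, assumed baseline correlation 0.5, 8,004 runs per cell, Monte Carlo SE about 0.0025). Type I error for the same four ICCs:

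| Analysis | ICC 0.01 | 0.02 | 0.05 | 0.10 |
|---|---|---|---|---|
| Planned ANCOVA | 0.053 | 0.058 | 0.060 | 0.072 |
| Partially nested REML, Satterthwaite df, cohort variance unbounded | 0.050 | 0.052 | 0.047 | 0.050 |
| Same, cohort variance bounded at zero | 0.043 | 0.046 | 0.041 | 0.047 |
| CR2 cluster-robust variance | 0.051 | 0.052 | 0.047 | 0.051 |

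With 13 cohorts of mixed size 3 to 7, at ICC 0.05 and 0.10, the ANCOVA gave 0.062 and 0.076 and the nested model 0.054 and 0.053. A second simulation of the planned ANCOVA (20,000 runs per setting, cohorts of 3 to 7) gave 0.052, 0.054, 0.066 and 0.074 at the four ICCs, and 0.050 at ICC 0.

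**Larger effect.** At the 9.2 points reported in section 9.2 from the earlier trial, d = 9.2/6.6 = 1.39 and power is 1.00 throughout.

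**The case against.** The omission is not in doubt; its importance can be disputed.

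- **The ICC is assumed.** Nothing in the documents anchors 0.01 to 0.10, and at 0.01 to 0.02 the excess type I error is only 0.2 to 0.5 percentage points. This stands: the text establishes the omission and its direction, but not a material effect.
- **The null is a particular one.** Participants are randomized individually. If FORT-A changes nobody's outcome, and shared sessions therefore create no correlation, the ANCOVA holds about 5%. This stands as a condition on every type I figure here. Interval coverage, however, does not depend on the average effect being zero.
- **The power loss is overstated without the covariate.** The plan adjusts for baseline ODI. At m = 5, a baseline correlation of 0.19, 0.23, 0.33 or 0.43 brings valid power back to 0.80 for the four ICCs, and 0.5 gives 0.83 to 0.89. At low ICC most of the shortfall is the cost of fewer degrees of freedom. This largely stands, so power is a secondary point. Adjustment does not remove the type I inflation: the simulated rates above already include a correlation of 0.5.
- **Usual care may be grouped too.** Section 6.2.2 speaks of filling PRC cohorts. If those were equally correlated, the problem would grow: at m = 5 and ICC 0.05, VR = 1.20 and type I error is 7.4%.
- **Providers are a further source of correlation.** Section 5.2 has four group providers rotating across cohorts. A cohort term alone does not capture this, so the corrected test is valid only if provider effects are small.

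**Conclusion.** The concern holds as a conditional one and should be fixed. The plan analyses a group-delivered arm as if its members were independent, and its sample size makes the same assumption. With cohorts of 5, 65 analysed per arm, independent usual-care participants and an assumed ICC of 0.01 to 0.10, the planned standard error is understated by a factor of 1.01 to 1.10 (√1.02 to √1.20). The corresponding type I error is 5.2 to 7.4%, when the average effect is zero but cohorts differ. The effect is negligible at the bottom of that range and material from about 0.05. Bias is not an issue, and at the earlier trial's effect size neither is power. What is at stake is the error rate of the primary test and the coverage of its interval, which matters because section 9.2 reads the result against a 3.3-point threshold.

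**What to change.** In section 9.6, prespecify the primary 12-month ODI comparison as a partially nested ANCOVA: a random cohort effect in FORT-A only, arm-specific residual variances, and Satterthwaite or Kenward-Roger degrees of freedom. Keep the cohort term even if its variance is estimated near zero, preferably without a zero bound, since the bounded fit was slightly conservative. CR2 with Satterthwaite degrees of freedom is an acceptable and simpler alternative.

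Also:
- Carry a FORT-A cohort identifier in the analysis data set. It would reveal arm, and section 3 states that "The PI, Independent Evaluators, and Biostatistician will be blind to the condition of all participants until data lock", so unblinded staff should hold it until then.
- Confirm that the PRC cohorts in section 6.2.2 share no treatment sessions before coding usual-care participants as singletons.
- State how FORT-A participants who never start are coded, and carry cohort through any multiple imputation.
- In section 9.2, give power over an assumed ICC range.

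The cost is SAP wording and one variable. That variable can probably be reconstructed from the activity logs (section 5.4), the recording labels (section 6.2.3.1) and the group notes in the medical record (section 5.2), so new data collection may not be needed. The price in precision is an interval about 3, 4, 7 or 13% wider than the planned one at m = 5 for ICC 0.01, 0.02, 0.05 or 0.10; about 3% is paid even where the correction is barely needed.

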1. STUDY OBJECTIVES

1.1 Primary Objectives

Hypothesis 1: FORT-A will result in significantly greater improvements in pain management among PRC Veterans compared to standard PRC care based on the primary outcome measure of self-report disability (Oswestry Disability Index) at both short- (pre- to post-treatment) and long-term (6/12-month) follow-up.

Hypothesis 2: FORT-A will also result in significant improvements on secondary pain management outcomes compared to PRC, including pain coping (intensity/ cognitions), emotional distress (depression, PTSD, anxiety), and objective disability (functional capacity, gait) at short- and long-term follow-up.

Hypothesis 3: We hypothesize that FORT-A will result in significantly lower rates of opioid recidivism compared to standard PRC treatment based on timeline followback interview at 12-months follow-up.

Hypothesis 4: We also hypothesize that FORT-A will result in significantly less opioid recidivism compared to PRC treatment based on secondary measures of opioid medications including Medication Event Monitoring System (MEMS), pill counts, and consultation with prescribing providers/ documentation in the VA Electronic Health Record (CPRS).

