Secondary Hypothesis: FORT-A participants will demonstrate significantly lower rates of opioid recidivism than TAU participants at one-year post-treatment. Opioid and other pain medication use is being assessed using a timeline follow-back interview and MEMS caps (with the timeline follow-back as the primary measure based on its documented reliability and validity; Sobell & Sobell, 1992).

- ***We are currently discussing the value of adding urine tox screens at pre-treatment, post-treatment, and one-year follow-up.*** The study team previously eschewed the use of a urine tox screen for this research endpoint

because of concerns about the validity and sensitivity of urine tox screens for opioid use. However, in consultation with [name] and the VA Opioid Safety Initiative, we have identified certain tests applied to a urine sample that can reliably and validly illuminate opioid use patterns. We are still examining this addition and how we might be able to partner with the VA to add this to our outcome battery (after discussing this with NCCIH more, of course) without additional cost. The VA system has increased implementation of urine tox screens for opioid using Veterans (see <http://www.veterans.senate.gov/imo/media/doc/VA%20Clancy%20Testimony%203.26.20151.pdf>). However, studies in the PRC population using urine tox screening risk high attrition because Veterans may feel mistrusted. Because timeline followback has shown reliability and validity in the past, we have chosen to stay with this method for tracking opioid use and recidivism to opioid use. However, we will have access to electronic medical records (CPRS) to identify new opioid prescriptions in the VA system and [name] and [name] can access the *Prescription Access in Texas* website (see <https://www.texaspatx.com/Tutorial/Doc/PATIFAQs.pdf>), the Texas State prescription monitoring program, to identify opioid prescriptions dispensed outside of the VA. We are able to keep all opioid medication use confidential as part of the research record and hope that this will increase the reliability and validity of reporting.

Tertiary Hypotheses:

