AIM 2: Assess the efficacy of FORT-A for decreasing the rate of opioid medication recidivism compared to standard PRC care in a sample of OEF/OIF/OND polymorbid LBP Veterans. To examine our primary hypothesis, we will compare the rate of opioid medication recidivism between the two groups monthly from baseline to 12-month follow-up. As noted above, 30-40% of TAU participants are expected to meet criteria for opioid recidivism (use of any opioid medication for 3 days or more in the last 30 days at each assessment). A statistically significant main effect will be interpreted as the groups exhibiting differential change in regards disability. Secondary analyses will be conducted using growth curve modeling (i.e., mixed effects hierarchical regression with polynomial change parameters to model differences in the trajectory of opioid use over time between the groups by time).

EXPLORATORY AIM 3: To examine the role of helplessness and perceived burdensomeness in predicting the trajectory of change over time, we will use latent

growth curve modeling. We will first model the trajectory of change in the two primary outcomes as a function of group (Aim 1 and Aim 2). We will then model the trajectories of helplessness and perceived burdensomeness as a function of group. Assuming both associations are observed (i.e., that group status is related to changes in the outcomes and the mediators), we will conduct hierarchical entry of group status and each mediator to examine if group status is still associated with outcome after adjusting for changes in the mediators. This will allow us to assess the role of the mediators in predicting the outcome and the proportion of change trajectory attributed to changes in these mediators.

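### The plan places the Aim 2 opioid comparison monthly in one section and at 12 months in others, and the main analysis names no method for repeated records on the same Veteran

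*Combined protocol and SAP*

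**What the plan says.** Section 9.6 opens with one modelling framework for all aims: "To examine our aims and hypotheses we will utilize the generalized linear model, which allows specification of an appropriate distribution for each outcome". It gives the binomial distribution with logit link for presence/absence outcomes.

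For the main Aim 2 analysis it then says "we will compare the rate of opioid medication recidivism between the two groups monthly from baseline to 12-month follow-up", with recidivism defined over the last 30 days at each assessment. The decision rule is "A statistically significant main effect will be interpreted as the groups exhibiting differential change in regards disability", which repeats the Aim 1 sentence word for word. The within-person model comes only after that: "Secondary analyses will be conducted using growth curve modeling (i.e., mixed effects hierarchical regression with polynomial change parameters to model differences in the trajectory".

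Other sections time the comparison differently. Hypothesis 3 in section 1.1 expects "significantly lower rates of opioid recidivism compared to standard PRC treatment based on timeline followback interview at 12-months follow-up". Section 9.1 says "FORT-A participants will demonstrate significantly lower rates of opioid recidivism than TAU participants at one-year post-treatment". The Aim 2 statement in the précis and the definition in section 3 count use in any 30-day period, which could also mean ever during follow-up.

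Section 9.2 takes 65 per group, 12 data collection periods and a significance level of 0.05. It credits the frequent assessment with supplying the power, and gives 0.80 for 45% versus 22.5%.

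**The concern.** Twelve yes/no records from one Veteran are not twelve independent observations. A Veteran who has gone back to opioids in one month is likely to be using them in the next.

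The data collection adds to this. Calls are monthly within one week either way (section 6.2.4) and each timeline followback covers 30 days (section 9.5.2). A call one week late followed by a call one week early leaves about 30 − 14 = 16 days between them, so about 14 days can count in both records.

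An ordinary binomial generalized linear model ignores this correlation and gives a standard error that is too small. Section 9.6 names a mixed model for the secondary Aim 2 analysis and none for the main one, so an analyst who follows it literally could fit exactly that model. The alternatives (month 12, ever, or monthly) and the variance method stay open until the data are seen. What is at stake is a claim that the program reduces, or raises, return to opioid use when it does neither.

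**Working it through.** **Inputs.** From section 9.2: 65 per arm, 12 records per Veteran, alpha 0.05, rates 45% and 22.5%. From section 9.6: control rate 30–40%, so 35% was used as its midpoint in the simulation. Two-sided testing is assumed, since sidedness is stated only for the Oswestry calculation. The within-Veteran correlation ρ is assumed and varied.

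**Step 1: the plan's own power figure.** Treat each Veteran as one binary record.

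- Difference: 0.45 − 0.225 = 0.225; mean rate 0.3375.
- Unpooled SE = √[(0.45×0.55 + 0.225×0.775)/65] = 0.0806.
- Pooled SE = √[2×0.3375×0.6625/65] = 0.0829.
- Power, unpooled: Φ(0.225/0.0806 − 1.96) = 0.80.
- Power, pooled under the null: Φ[(0.225 − 1.96×0.0829)/0.0806] = 0.78.

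The stated 0.80 is reproduced. With 65×12 = 780 independent records per arm, power would exceed 0.999, so the figure does not come from independent monthly records. A correctly clustered monthly analysis with 65 per arm comes near 0.80 only if ρ is close to 1 (0.82 at ρ = 0.9, 0.78 at ρ = 1), which amounts to one record per Veteran.

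**Step 2: error if 12 monthly records enter an ordinary binomial model.** With equal correlation between months, the design effect is DE = 1 + (12 − 1)ρ. The model-based SE is 1/√DE of the correct one, and the actual two-sided error is 2×[1 − Φ(1.96/√DE)].

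| Assumed ρ | DE | Model SE / correct SE | Actual type I error |
|---|---|---|---|
| 0.05 | 1.55 | 0.80 | 11.5% |
| 0.1 | 2.1 | 0.69 | 17.6% |
| 0.3 | 4.3 | 0.48 | 34.5% |
| 0.5 | 6.5 | 0.39 | 44.2% |
| 0.8 | 9.8 | 0.32 | 53.1% |

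Counting baseline as a thirteenth record raises these slightly (12.1% at 0.05, 54.7% at 0.8).

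**Step 3: checks.** Beta-binomial simulation under no effect (65 per arm, 12 records, 40,000 runs, rates 35% and 45%) gave 17–18%, 35%, 44% and 54% at ρ = 0.1, 0.3, 0.5 and 0.8. A Veteran-level test on the same data gave 4.8–5.2%. If correlation instead decays with time (first-order autoregressive, 0.3 to 0.95), the formula gives 14% to 53%. With one record per Veteran, the simulated error was 5.3%.

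**The case against.** A reader might infer that the plan specifies an analysis that treats the monthly records as independent, and so carries a false-positive risk somewhere between one in six and one in two. The documents do not support that, for three reasons.

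- Independence is never stated. The generalized linear model sentence is a general remark about outcome distributions, and its binary example is daily opioid use. The authors name a mixed-effects model for the opioid trajectory, so they know the data are repeated.
- Sections 1.1 and 9.1 and the reproduced power all fit one record per Veteran, where nothing is inflated.
- Any inflation figure needs a correlation that the plan does not give; at ρ = 0.02 the error would be only 7.6%.

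A reader might also take the monthly wording to mean twelve separate tests at 0.05. The rule refers to a single main effect, which does not fit that reading.

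All of this stands. What remains is that the analysis section itself says monthly and assesses recidivism at each assessment, and section 9.2 credits the 12 collections with the power, which requires them to enter the test. For Aim 1, section 9.6 clearly specifies one 12-month comparison; for Aim 2 it does not. The word disability in the decision rule is a drafting slip with no effect on the error rate, but it makes the rule refer to the wrong outcome.

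**Conclusion.** The Aim 2 estimand is inconsistent between sections 1.1 and 9.1 (12 months or one year) and section 9.6 (monthly). Section 9.2 cites 12 collections but reports the power of a single one. The main analysis names no method for repeated records.

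The consequence is conditional. If 12 monthly records went into an ordinary binomial model, type I error would be about 12% at an assumed within-Veteran correlation of 0.05 and about 53% at 0.8. With one record per Veteran, or a clustered analysis, it is about 5%.

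This should be fixed but does not threaten the trial's main result. Sections 3 and 9.1 treat opioid recidivism as secondary, and section 9.6 names the Oswestry score as the one primary endpoint. Section 2.2 and the Aim 3 text do loosely call opioid use a primary endpoint or outcome, which is a further reason to settle the wording.

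**What to change.** Before data lock, state one Aim 2 estimand and bring sections 1.1, 9.1, 9.2 and 9.6 into line with it, along with the any-30-day-period definition in the précis and section 3.

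- **If monthly:** replace the ordinary generalized linear model as the main analysis with one named model. An example is a binomial GEE with logit link, robust standard errors clustered on Veteran and a small-sample correction. A logistic mixed model with a Veteran random intercept is an alternative, but its odds ratio is Veteran-specific, so the two are not interchangeable. Test one prespecified group contrast over the post-treatment months.
- **If month 12:** use one record per Veteran; the generalized linear model then suffices.
- **Either way:** change disability to opioid recidivism in the Aim 2 decision sentence.

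The cost is SAP wording and, for the monthly choice, a wider and correct confidence interval. Reading 45% and 22.5% as monthly rates, power with the correct standard error at 65 per arm is 0.96 at ρ = 0.5 and 0.86 at ρ = 0.8; at 65×0.7 = 45.5 per arm after 30% attrition it is 0.88 and 0.72. With one record per Veteran it is 0.78, or about 0.63 at 45.5 per arm. Section 9.2 should give the figure for the estimand chosen.
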